	
area where study drug was applied on Day 1, even if the % BSA improves over the course of the first 2 weeks (14 days) of treatment. Between Day 15 (after the maximal use application and collection of PK samples) and Day 28, the study drug will only be applied to the involved areas. The last application of study drug will be given the evening before the final visit (V6).
 
An independent Data Safety Monitoring Board (DSMB) will facilitate the management and identification of potential safety concerns, on a regular basis, that could affect the safety of trial subjects, and will examine whether the information collected during these periodic intervals is consistent with knowledge about the product's safety (e.g., unanticipated adverse events). The DSMB will also assess whether revisions to the study protocol and/or consent are required, and will evaluate the overall progress of the study. Details regarding the policies and procedures of the DSMB and intervals and data to be evaluated will be described in the DSMB Charter.

Description of Test Article, Dosage, and Administration	
MM36 1% Ointment for topical administration is a white petrolatum based ointment containing MM36 1% weight/weight (w/w), Corporate Confidential Information Each gram of MM36 1% w/w ointment contains 10 mg of active MM36.
 
All subjects will receive active study drug and the dosage will be based on % BSA involvement (intended area to be treated). The study drug will be applied twice daily (approximately 12 hours apart) for up to 4 weeks (28 days).

Study Centers	Up to 12 investigational sites in the United States (U.S.) , Honduras, and Panama will participate.

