3.3 Criteria for Evaluation

3.3.1 Primary Endpoints

Determination of plasma concentrations, of the parent compound MM36 and its metabolites, after the first topical application of MM36 and after two weeks of twice daily application (steady state).

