7.4 Visit 4/Day 15 (± 1)

It is estimated that this visit will take approximately 8 hours to complete.

- Interview
 - Update medications (those taken since the last visit);
 - Assess for AEs; and
 -
- Assessments
 - Assess application sites;
 - Perform abbreviated physical exam (only as applicable for evaluation of AEs);
 - Obtain weight;
 - Obtain and record vital signs;
 - Assess BSA for affected AD and record on body grid;
 - Photograph AD sites as applicable;
 -
 - Compliance check (weight check of study drug and review diary completion).
- Sample Collection
 - Collect a blood sample for PK prior to application at the study clinic and again at 1 hour (± 15 minutes), 4 hours (± 30 minutes) and 8 hours (± 1 hour) post application.
- Instructions
 - Dispense study drug;
 - Review dosing procedure and have the parent/guardian (caregiver)/subject apply the study drug to the affected areas; and

- Schedule Return visit for 1 week (Day 22) and remind parent/guardian (caregiver) and subject not to apply study drug in the morning before the visit and to bring all used and unused study drug to next visit.

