8.4 Dosing

The subject (parent/guardian (caregiver) will be instructed on proper application of the study drug and will apply the initial application on Day 1 at the study site. The proper dose dispensing procedure and use of the study drug will be demonstrated and observed by study staff to ensure subject (parent/guardian (caregiver) understand the instructions.

- For each dosing period, the subject, under the supervision of the parent/guardian (caregiver), or the parent/guardian (caregiver), will dispense the required amount of ointment (by weight) using the measuring cup(s) provided.
- The subject should wash his/her hands both before and after applying study ointment. If applied by the parent/guardian (caregiver), they should also wash hands before and after applying study ointment, but will also wear non-latex gloves (provided by the Sponsor).
- The subject (parent/guardian (caregiver) will apply a thin layer of ointment to affected areas twice daily (approximately 12 hours apart) for 28 consecutive days.
- It is recommended that the ointment be applied after showering/bathing. The skin should be dry prior to application. Important: Subjects should not swim or bathe or wipe application area for a minimum of 20 minutes after application of ointment.
- The ointment should be rubbed in gently and completely, avoiding contact with the eyes.
- Subject's (parent/guardian (caregiver) will be instructed not to administer the study drug in the morning on the day of the study visit to avoid any effect of the study drug on the assessments.
- An adult (≥ 18 years of age) parent/guardian (caregiver) will verify if the study drug was weighed appropriately and applied as directed. Application details will be recorded in the electronic diary.

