11.4 Primary Analysis

11.4.1 Pharmacokinetics

Individual plasma concentrations of MM36 and its metabolites (MAP-15484, MAP15497 and MAP-15485) will be summarized descriptively using the arithmetic mean, standard deviation (SD), CV (%), median, minimum and maximum. Individual plasma concentration-time profiles of MM36 will be plotted on both a linear and a semi-logarithmic scale. Mean values will also be presented graphically. The following pharmacokinetic parameters will be analyzed for each subject and for each PK time point at which a sufficient (detectable) concentration of MM36 or its metabolites will be measured to permit their derivation. If there are sufficient concentration data above the level of quantitation the following pharmacokinetic parameters will be calculated:

- C_{max} = Maximum plasma concentration
- T_{max} = Time of maximum plasma concentration
- AUC_{0-last} = Area under the plasma concentration-time curve from time zero to time last (time of last quantifiable plasma concentration) [AUC_{0-t}]

The pharmacokinetic analysis will be implemented in SAS®, and conducted using Non-Compartmental Analysis (NCA) on plasma concentrations of MM36 in the subjects who will receive MM36 1% ointment and had evaluable plasma concentration-time profiles. PK parameters will be listed for all individuals. Descriptive summary statistics (number of observations (N), arithmetic mean, standard deviation (SD), CV%, median, minimum, maximum and geometric mean) will be reported for PK parameters. Individual elapse sampling time will be used in the pharmacokinetic analysis. C_{max} and t_{max} will be obtained directly from the experimental observations. $AUC_{(0-t)}$ will be calculated using the linear trapezoidal rule.

BLQ (< 0.2 ng/mL) samples will be set to zero for the summary of the statistics for concentration values. For the purpose of the NCA, BLQ set to zero before t_{max} and missing after t_{max} . Any quantifiable concentrations at pre-dose at Day 1 will be set to zero.

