7.9.7 Pharmacokinetic Analyses

The pharmacokinetic analysis will be conducted using non-compartmental analysis on plasma concentrations of MM36 and its metabolites (MAP-15484, MAP15497 and MAP-15485) in the subjects in the safety population who have PK data.

Individual plasma concentrations of MM36 and its metabolites will be summarized descriptively at Day 1 and Day 15 using the arithmetic mean, SD, CV%, median, min, and max. Individual plasma concentration-time profiles of MM36 and its metabolites will be plotted on both a linear and a semi-logarithmic scale at each visit. Mean values will also be presented graphically.

Plasma concentrations below the lower limit of quantitation (BLQ) (< 0.2 ng/mL) will not be considered quantifiable concentrations. BLQ values and quantifiable concentrations will be

summarized separately using summary statistics. Any quantifiable concentrations at pre-dose at Day 1 will be set to zero in both concentration summaries, as well as in PK parameter calculations. Plasma concentration-time profiles will display BLQ values as 0 ng/mL on the linear scale, and will omit BLQ values on the semi-logarithmic scale.

The following pharmacokinetic parameters will be analyzed for each subject at Day 1 and Day 15 if there are a sufficient number of quantifiable concentrations of MM36 or its metabolites to permit their derivation.

C_{\max}	Maximum plasma concentration C_{\max} = BLQ if concentrations are BLQ at all time points
T_{\max}	Time of maximum plasma concentration T_{\max} will be calculated if at least one quantifiable plasma concentration is detected in the time interval. Individual elapsed sampling times will be used. If the maximum concentration is observed pre-dose, T_{\max} will be considered 0 hours.
$AUC_{0-\text{last}}$	Area under the plasma concentration-time curve from time zero to the time of last quantifiable plasma concentration $AUC_{0-\text{last}}$ will be calculated if at least two consecutive quantifiable plasma concentrations are detected in the time interval. Area will be computed using the linear trapezoidal rule with individual elapsed sampling times and observed concentrations. BLQ values will be set to zero before T_{\max} and missing after T_{\max} .

Descriptive summary statistics (n, arithmetic mean, SD, CV%, median, min, max, and GM) will be reported for PK parameters. Individual plasma concentrations and PK parameter values will be included in by-subject listings.

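### The only planned area measure, AUC0-last, stops at each child's last quantifiable sample (nominally 8 h at most), so on Day 15 it normally falls short of exposure over the 12 h dosing interval

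*SAP*

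**What the plan says.** SAP 7.9.7 lists three pharmacokinetic parameters for Day 1 and Day 15: Cmax, Tmax and AUC0-last. The last is defined as "Area under the plasma concentration-time curve from time zero to the time of last quantifiable plasma concentration", and Protocol 11.4.1 has the same three. No AUC over the dosing interval, fixed-interval AUC or extrapolation appears in either document.

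The calculation rule is: "Area will be computed using the linear trapezoidal rule with individual elapsed sampling times and observed concentrations". Results below 0.2 ng/mL count as zero before Tmax and as missing after it. At least two consecutive quantifiable concentrations are needed before an area is computed.

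Protocol 8.4 has the ointment applied "twice daily (approximately 12 hours apart"). Protocol 7.4 draws blood on Day 15 before the clinic application, at 1 hour, and then at "4 hours (± 30 minutes) and 8 hours (± 1 hour) post application". There is no 12 h sample.

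The primary endpoint (Protocol 3.3.1, SAP 6.1.1) is plasma concentration after the first application and "after two weeks of twice daily application (steady state"). The primary objective (SAP 3.1) is the degree of systemic exposure under maximal use.

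**The concern.** The trial exists to describe systemic exposure, and Day 15 is where the plan treats exposure as being at steady state. At steady state the natural area summary is the AUC over one dosing interval. The plan has no such parameter. Its one area measure leaves out at least the last quarter of the interval, nominally the last third, and more where late samples are BLQ.

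Two consequences follow if AUC0-last is used as exposure per dose:

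- An individual child's figure will normally be too low.
- Two children with nearly the same curve can have areas over different lengths of time, because one is just above 0.2 ng/mL at 8 h and the other just below.

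**Working it through.** The documents give no half-life, absorption rate or expected AUC, so there is no planned figure to reproduce.

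**Inputs from the documents.** Interval 12 h (Protocol 8.4); nominal times 0, 1, 4 and 8 h (Protocol 7.4); linear trapezoid, limit 0.2 ng/mL and the BLQ rule (SAP 7.9.7).

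**Assumed.** One-compartment, first-order absorption at steady state; elimination half-life 2–24 h; absorption half-life 1–11 h.

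**Step 1: share of the interval covered.** This equals the share of AUC0-12 for a flat profile.

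- Last quantifiable sample at 8 h: 8/12 = 66.7% (7 h: 58.3%; 9 h: 75.0%)
- At 4 h: 4/12 = 33.3%
- At 1 h, possible if the pre-dose sample is also quantifiable: 1/12 = 8.3%

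**Step 2: assumed profile.** Up to a constant,

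C(t) = ka/(ka − ke) × [exp(−ke·t)/(1 − exp(−12ke)) − exp(−ka·t)/(1 − exp(−12ka))], with true AUC0-12 = 1/ke.

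**Step 3: one corner in full.** Elimination half-life 2 h, absorption half-life 1 h, so ke = 0.34657, ka = 0.69315 and 1/ke = 2.88539.

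- C(0) = 0.03126, C(1) = 0.43642, C(4) = 0.38291, C(8) = 0.11917
- Trapezoids: 0–1 h 0.23384; 1–4 h 1.22898; 4–8 h 1.00415
- To 8 h: 2.46697/2.88539 = 0.85499, quoted as 85%
- To 4 h: 1.46282/2.88539 = 0.507, or 51%
- Pre-dose value placed at 12 h: the 8–12 h piece is 4 × (0.11917 + 0.03126)/2 = 0.30086, giving 2.76783/2.88539 = 0.959, or 96%

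**Step 4: whole assumed range (49 profiles).**

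| Measure | Share of true AUC0-12 |
|---|---|
| Planned trapezoid to 8 h | 67–85% |
| Exact area to 8 h | 67–91% |
| Planned trapezoid to 4 h | 33–51% |
| Trapezoid to 12 h, pre-dose as 12 h value | 96–100% |

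Comparing the first two rows, part of the shortfall at the fast end is trapezoid error and not truncation. With wider assumptions (half-life 2–48 h, ka 0.1–1.0 per h), the exact shares are 67–93% to 8 h and 33–65% to 4 h.

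In all 49 profiles the 8 h concentration was at or above the pre-dose one. A child BLQ at 8 h should therefore be expected to be BLQ pre-dose too, and the 96–100% row does not apply to that child.

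**Step 5: effect of the end point, with and without a BLQ rule.** Two invented children have a BLQ pre-dose value, 0.50 ng/mL at 1 h and 0.40 at 4 h. Child A has 0.21 at 8 h; child B is BLQ there.

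- AUC0-last, A: 1 × (0 + 0.50)/2 + 3 × (0.50 + 0.40)/2 + 4 × (0.40 + 0.21)/2 = 0.25 + 1.35 + 1.22 = 2.82
- AUC0-last, B: 0.25 + 1.35 = 1.60. Ratio 2.82/1.60 = 1.76
- AUC0-8, BLQ = 0: A 2.82; B 1.60 + 4 × (0.40 + 0)/2 = 2.40. Ratio 1.18
- AUC0-8, BLQ = 0.1: A 0.30 + 1.35 + 1.22 = 2.87; B 0.30 + 1.35 + 1.00 = 2.65. Ratio 1.08
- AUC0-12, BLQ = 0: A 2.82 + 4 × (0.21 + 0)/2 = 3.24; B 2.40 + 0 = 2.40. Ratio 1.35
- AUC0-12, BLQ = 0.1: A 2.87 + 4 × (0.21 + 0.1)/2 = 3.49; B 2.65 + 4 × 0.1 = 3.05. Ratio 1.14

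If BLQ after Tmax stayed missing, child B's 8 h and 12 h values would both drop out and the area would stop at 4 h again. The new parameters need their own BLQ value.

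**The case against.** A reader might infer that Day 15 exposure is reported only through a truncated area. It is not. The primary endpoint is the concentrations themselves. SAP 7.9.7 summarises them at each day, plots individual and mean profiles, reports Cmax and Tmax, and lists every value by subject. AUC0-last is correctly labelled and is nowhere called exposure per dosing interval. SAP 4.2 says the sample size is not driven by inference, and no stated decision hangs on this parameter. All of that stands, and makes this a gap in the parameter set and not a miscalculation.

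A reader might also infer that areas cannot be compared between children at all. For those quantifiable at every sample, the end point is 8 h ± 1 h and comparability is largely intact. The problem is confined to children whose last quantifiable times differ.

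Nor can one conclude that group means are understated. Children without two consecutive quantifiable values get no area. Those tend to be the least exposed, so that rule can push group means upward.

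Finally, using the pre-dose value at 12 h asks for more than the words steady state. The morning application is withheld until the visit (Protocol 7.3, 8.4), so the gap from the previous dose may exceed 12 h. That dose is applied at home, and the amount can rise if disease spreads (Protocol 6.9.3). In support, the treated area does not shrink before the Day 15 samples (Protocol 6.9.1, 6.9.2), and the diary records application times (Protocol 6.10). These limits call for labelling and for reporting the actual interval; they do not remove the value of the parameter.

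**Conclusion.** The point holds as a limited one. AUC0-last ends before the 12 h interval does, so as a per-child measure of Day 15 exposure per dose it is normally low. The planned trapezoid gives about 67–85% of AUC0-12 with a quantifiable 8 h sample and 33–51% when 4 h is the last. These shares rest on assumed one-compartment steady-state profiles; no half-life is given in the documents.

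Between children with different last quantifiable times, the areas cover different intervals. How often this will occur cannot be told from the documents, and the direction of bias in group means is not settled.

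Adding the missing parameters is a cheap improvement. It uses a steady-state premise the plan already states and blood it already draws.

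**What to change.** In SAP 7.9.7:

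1. Keep AUC0-last as planned.
2. Add Day 15 AUC0-12 by the linear trapezoidal rule, with the Day 15 pre-dose concentration as the 12 h value, labelled as assuming steady state.
3. Add AUC0-8 over the same fixed interval for every child on Day 1 and Day 15, and state how samples taken at 7–9 h are brought to 8 h.
4. For these two parameters only, replace the rule that BLQ after Tmax is missing with a stated value, for example zero, with half the quantitation limit (0.1 ng/mL) as sensitivity.
5. Report from the diary the actual time between the previous application and the Day 15 pre-dose sample.
6. Tabulate children by last quantifiable time, including those with no AUC.

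Protocol 11.3.1 lets the SAP carry modifications if finalised before database lock. The cost is two derived parameters and a short table, with no extra blood. The downside is reliance on steady state and on a BLQ convention. Where the 8 h and pre-dose values are both BLQ, AUC0-12 is only approximate; for child B above it is 2.40 or 3.05 ng·h/mL, depending on the convention.

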7.9.8 Efficacy Analyses

7.9.8.1 Primary Efficacy Analysis

There is no primary efficacy analysis.

7.9.8.2 Secondary Efficacy Analysis

There is no secondary efficacy analysis.

CONFIDENTIAL

7.9.8.3 Exploratory Efficacy Analyses

Corporate Confidential Information

[figure not shown]
CONFIDENTIAL

Corporate Confidential Information

CONFIDENTIAL

7.9.8.3.4.2

Corporate Confidential Information

7.9.9 Safety Analyses

7.9.9.1 Extent of Exposure

The extent of exposure to study drug will be summarized by total number of days of exposure, total number of applications, percent compliance, and total amount of study drug applied. Total number of applications will be determined by the number of entries in the dosing diary. Total number of days of exposure will be computed as follows:

Days of Exposure = Date of Last Application – Date of First Application + 1.

To compute percent compliance, total number of expected applications will be calculated by:

Expected applications = $2 * (\text{Study Completion/Discontinuation Date} - \text{Date of First Application})$.

If the total number of expected applications exceeds 58 then it will be set to 58. Percent compliance will be calculated from total number of applications and total number of expected applications as follows:

Percent Compliance = $100 * (\text{Total Applications}/\text{Expected Applications})$.

Percent compliance will not be calculated for subjects who are lost to follow-up.

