4 STUDY DESIGN

4.1 General Description

This multicenter, open-label study, will evaluate the pharmacokinetics, safety, tolerability, and the exploratory efficacy of MM36 1% ointment when applied twice daily for up to 4 weeks in subjects 2 to < 18 years of age with atopic dermatitis, at the upper range of disease severity. This study will also evaluate the systemic availability of MM36 1% when applied topically under maximal use conditions.

Following screening (within 30 days prior to the first dose of study drug) and confirmation of study qualification, subjects will be registered and assigned (V2) to one of three treatment groups based on the subject's age at Screening (V1). The first dose of study drug will be applied in the study clinic (V2/Day 1) and blood samples will be collected for evaluation of PK prior to the first application (0 hours) and at 1 hour (\pm 15 minutes), 4 hours (\pm 30 minutes) and at 8 hours (\pm 1 hour) after application of study drug. On Day 15, the study drug will again be applied in the study clinic, and blood samples will be collected for PK prior to dosing and at 1 hour (\pm 15 minutes), 4 hours (\pm 30 minutes) and at 8 hours (\pm 1 hour) after application of study drug.

Corporate Confidential Information

At Screening (V1) and Baseline (V2), subjects with atopic dermatitis that are 2 to less than 12 years of age (Group 2 and 3) must have a treatable area comprising \geq 35% BSA involvement (excluding scalp and venous access areas), and subjects 12 years of age and older (Group 1) must have \geq 25% BSA involvement (excluding scalp and venous access areas) (i.e., maximal use conditions). The same (or greater, BSA if area involved expands) amount of study drug topically applied at baseline will continue to be applied twice daily, to the same area where study drug was applied on Day 1, even if the % BSA improves over the course of the first 2 weeks (14 days) of treatment. Between Day 15 (after the maximal use application and collection of PK samples) and Day 28, the study drug will only be applied to the involved areas. The last application of study drug will be given the evening before the final visit (V6). Refer to [Figure 1](#).

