4.6.1 Criteria for Premature Discontinuation

4.6.1.1 Discontinuation from Treatment

A subject must be permanently discontinued from the study drug for any of the following reasons:

- The subject becomes pregnant;
- Allergic or adverse reaction to the study drug;
- Clinically significant adverse event, which in the opinion of the Investigator, or DSMB, would put the subject at unnecessary risk if dosing was continued; or
- The subject's atopic dermatitis worsens and requires alternative or supplemental medication during the study.

If a subject is discontinued from treatment, they should continue to be followed in the study. If subject refuses to stay in the study, then they will be encouraged to complete the V6 (Week 4/ET visit).

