6.10 Dosing Diary

The subject/parent/guardian (caregiver) will be provided with an electronic dosing diary to record the time and amount of each study drug application. The importance of adherence to the study schedule will be reinforced at each study visit.

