8.5 Compliance

The parent/guardian (caregiver)/subject will record the amount of drug used at each application and application location in the electronic diary. All used and unused study drug will be returned at all protocol-specified visits for study drug inventory and assessment of subject adherence.

The weight of the study drug will be measured before it is dispensed and after it is returned at Visit 3/Week 1, Visit 4/Week 2, Visit 5/Week 3 and Visit 6/Week 4. Each dispensing and return of study drug as well as the weight of study drug will be documented in the eCRF. The dispensing and return of all study drug will be recorded on the study drug dispensing log. The subject number/initials and the initials and date of the person dispensing and receiving the returned medication will be documented on this form.

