11.3.3 Treatment Compliance

The Parent/guardian (caregiver)/Subject will record all applications made or missed in the electronic diary. Subject compliance during the overall treatment period and by visit will be summarized.

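### SAP 7.9.9.1 can misstate the application count and percent compliance, because it counts all diary entries as applications and ends expected dosing at a study date

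*SAP*

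**What the plan says.** SAP 7.9.9.1 builds percent compliance from two counts.

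- **Numerator.** "Total number of applications will be determined by the number of entries in the dosing diary". Nothing separates applications made from applications missed.
- **Denominator.** Expected applications are twice the number of days from first application to the study completion or discontinuation date. There is a cap: "If the total number of expected applications exceeds 58 then it will be set to 58". The percentage is not calculated for subjects lost to follow-up. No other exception is given.

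The protocol describes the diary in more than one way. Section 11.3.3 says the family "will record all applications made or missed in the electronic diary", and promises compliance both overall and by visit. Section 6.10 describes an "electronic dosing diary to record the time and amount of each study drug application". Section 8.5 says the family "will record the amount of drug used at each application and application location in the electronic diary". Neither 6.10 nor 8.5 mentions misses.

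On stopping, Protocol 4.6.1.1 says: "If a subject is discontinued from treatment, they should continue to be followed in the study". The SAP is built the same way: 7.1 keeps off-treatment assessments in the summaries, and 7.9.3 tabulates treatment discontinuation and study discontinuation separately.

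**The concern.** The numerator rule and Protocol 11.3.3 do not fit together. Read literally, a family that logs each miss adds an entry for each miss, and the SAP counts those entries as doses given. The most conscientious reporters could then appear fully compliant.

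The denominator is tied to leaving the study, but the quantity of interest is tied to being on treatment. For a child who stops treatment and stays in follow-up as the protocol asks, expected applications keep accruing after dosing has ended. A child with the same dosing who also leaves the study gets a short denominator. The two percentages answer different questions, yet they enter one summary.

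Few other planned outputs would reveal a misstated count. Days of exposure is last minus first application date plus one, so gaps do not show. SAP 7.9.4 says protocol deviations will not be summarized. The by-visit compliance promised in Protocol 11.3.3 is missing from SAP 7.9.9.1, although SAP 5 declares no changes to the planned analyses.

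**Working it through.** **Inputs.** Twice-daily application for 28 days (Protocol 8.4); last application the evening before the final visit (Protocol 4.1); final visit Day 29 ± 1 (Schedule of Activities); cap of 58 (SAP 7.9.9.1). The numbers of misses and the stopping days below are illustrative assumptions, since the documents give none.

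**1. The plan's own figure.** Expected = min(58, 2 × (end day − 1)).

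- Final visit Day 28: 2 × 27 = 54
- Final visit Day 29: 2 × 28 = 56
- Final visit Day 30: 2 × 29 = 58

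The cap of 58 is therefore the latest in-window visit. In each case the result equals twice-daily dosing through the evening before, so a completer who makes every application scores exactly 100%.

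**2. Numerator, if a miss is stored as an entry.** Completer at Day 29, 56 expected, all misses logged. The SAP result is 56/56 = 100% in every row.

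| Misses logged | Applications made / expected |
|---|---|
| 3 | 53/56 = 94.6% |
| 6 | 50/56 = 89.3% |
| 10 | 46/56 = 82.1% |
| 14 | 42/56 = 75.0% |

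Each logged miss adds 1/56 = 1.8 percentage points. If misses create no entry, the error is zero.

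**3. Denominator, for a child who stops treatment.** Two children each make all 18 applications on Days 1-9 and then stop.

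- Followed to Day 29: 18 / (2 × 28) = 18/56 = 32.1%
- Leaves the study on Day 10: 18 / (2 × 9) = 18/18 = 100%

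The same pattern with other stopping days, fully dosed and followed to Day 29: stop after Day 7, 14/56 = 25%; after Day 14, 28/56 = 50%; after Day 21, 42/56 = 75%. Each would be 100% if the child left the study the next day.

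**4. Exit on Day 1.** Expected = 2 × (1 − 1) = 0, so the percentage is undefined.

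**5. What the overall figure shows about Day 15.** For a Day 15 visit, 2 × 14 = 28 applications are due beforehand. Suppose 14 of 56 are missed and correctly counted. If all fall before Day 15, compliance in that period is 14/28 = 50%. If all fall after, it is 28/28 = 100%. The overall value is 42/56 = 75% both times.

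**The case against.** The strongest reply has four parts.

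- **The numerator error is conditional.** Protocol 6.10, 8.5 and Appendix A describe recording applications carried out, with time, amount and location. Section 11.3.3 is the only text that mentions misses, and it does not say that a miss becomes an entry. This stands: the count can be wrong, but the documents do not show that it will be. They do not rule it out either, and the SAP text has no safeguard.
- **Study dates are right for most children.** This stands for completers, as step 1 shows.
- **32% is a legitimate share of the planned regimen.** So it is, and 100% is a legitimate on-treatment figure. What cannot be defended is one variable that gives either, depending on whether the child stays in follow-up. The slash in the SAP's date term might be read to include treatment discontinuation, but SAP 7.9.3 treats the two events as distinct.
- **Other outputs help.** Days of exposure would be 9 for both children in step 3, and treatment discontinuation is tabulated with reasons. An attentive reader could identify early stopping. Logged misses would remain hidden in the count.

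A reader might go further and infer that reported dose delivery as a whole is wrong, or that the Day 15 pharmacokinetic results are compromised. The documents do not support this. Total amount applied is a separate summary: Protocol 11.3.4 frames it by weight, and Protocol 8.5 has tubes weighed at dispensing and return. The SAP does not state its derivation, but a missed dose would add nothing to a sum of amounts. Plasma concentrations do not depend on diary counts.

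A reader might also infer that a child whose skin clears by Day 15 is scored as non-compliant. That rests on a rule the documents leave open. Protocol 4.1 says that after the Day 15 samples "the study drug will only be applied to the involved areas", while 8.4 describes application for 28 days in a row. Neither says what happens when no involved area remains, and the period in question follows the pharmacokinetic sampling.

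**Conclusion.** The point holds for two outputs: the application count and percent compliance.

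- Compliance is overstated by 1.8 points per logged miss for a Day 29 completer, provided misses are stored as diary entries. With 14 such misses it reads 100% instead of 75%.
- For children who stop treatment early, the figure depends on whether they stay in follow-up: 32% or 100% for the same Day 1-9 dosing. This assumes that the date in the formula is a study date, which is its literal sense. How many children would be affected is unknown.
- A Day 1 exit is a rare case but leaves the formula undefined.

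For completers with no logged misses the formula is exact. The study is descriptive, so no inference is at risk. Even a corrected overall percentage cannot show whether twice-daily dosing was kept up before the Day 15 samples, which is the period the primary endpoint relies on. Only the omitted by-visit summary would show that.

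**What to change.** In SAP 7.9.9.1:

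1. Count only diary entries recorded as an application made, with a non-zero amount. List misses separately.
2. Keep the present formula for completers. For a subject who stops treatment early, set expected applications to the number of twice-daily applications scheduled from the first application up to the treatment stop, counted inclusively and never below 1. The date convention must be explicit. Putting the last application date (Day 9) into the existing subtraction gives 2 × 8 = 16 and 18/16 = 112.5%. Adding a full day for everyone would turn a perfect Day 29 completer into 56/58 = 96.6%.
3. If the share of planned applications is also wanted, report it on its own line.
4. Restore by-visit compliance as promised in Protocol 11.3.3, including the period from Day 1 up to the Day 15 pharmacokinetic visit.

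Separately, Protocol 4.1 and 8.4 should be reconciled on application after Day 15, so that the expected count rests on one stated rule.

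The cost is a few sentences of SAP text and a small programming change. It should be confirmed that the diary export separates made from missed entries and that a treatment stop date is captured; SAP 7.9.3 mentions the number and reason for treatment discontinuation, not the date. Reported compliance will be lower for children with logged misses and higher for treatment-stoppers who stay in follow-up.
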